8.2.2.6. Pregnancy Testing

Women of childbearing potential will have urine pregnancy testing approximately every 4 weeks throughout the study from screening through the end of study visit, and a serum pregnancy test at the screening visit, end of treatment/early termination visit, and end of study visit. During some follow-up visits, and in case of early termination, pregnancy testing will occur at home via a urine pregnancy test. Patients will report results of the home urine pregnancy test to clinical site study personnel during follow-up visit or phone visits.

8.2.3. Efficacy Procedures

All laboratory samples will be collected before the dose of study drug is administered.

Alcohol consumption within 48 hours and smoking or intense physical exercise within 24 hours, prior to blood sampling are discouraged.

Total cholesterol, calculated LDL-C, TG, and non-HDL-C will be directly measured by the central laboratory. Low-density lipoprotein cholesterol will be calculated using the Friedewald formula. If TG values exceed 400 mg/dL (4.52 mmol/L), LDL-C will be measured via the beta quantification method (rather than via the Friedewald formula). If the LDL-C value is less than

25 mg/dL (0.65 mmol/L), LDL-C will be measured via the beta quantification method (rather than the Friedewald formula). Non-HDL-C will be calculated by subtracting HDL-C from TC. High-density lipoprotein cholesterol (HDL-C) will be measured for assessing non-HDL-C but is not an efficacy variable for this study.

Detailed procedures of sample preparation, storage, and shipment are provided in the laboratory manual.

8.2.3.1. Lipid Panel

Fasting (at least 8 hours) blood samples will be collected at specified time points shown in [Table 1](#), [Table 2](#), and [Table 3](#), for assessment of the lipid profile, comprising calculated LDL-C, non-HDL-C, HDL, TC, and TGs. These samples will also be used for specialty lipid panel assessment when it is scheduled at the same time as the lipid panel assessment.

8.2.3.2. Specialty Lipid Panel

Fasting (at least 8 hours) blood samples will be collected at specified time points shown in [Table 1](#), [Table 2](#), and [Table 3](#) for assessment of the specialty lipid profile, comprising Apo B, ratio of Apo B/Apo A-1, and lipoprotein a (Lp[a]) as well as for Apo CIII. Apolipoprotein A-1 will be measured for assessing ratio of Apo B/Apo A-1 but is not an efficacy variable for this study. The specialty lipid panels will be assessed in the same sample that is collected for the lipid panel.

8.2.4. Drug Concentration and Measurements

Samples for drug concentration will be collected at visits listed in [Table 3](#). Any unused samples may be used for exploratory biomarker research or other investigations.

8.2.5. Anti-Drug Antibody Measurements and Samples

Samples for ADA assessment will be collected at time points listed in [Table 3](#). Any unused samples collected for ADA assessments may be used for exploratory biomarker research or other investigations.

Patients who exhibit a positive ADA assay response with a titer >240 in their last sample analyzed will not participate in any other studies or under any treatment with evinacumab and will be followed 3 to 6 months after EOS visit until the titers have returned to <240 or to within 2 dilution steps from the pre-treatment baseline titer.

8.2.6. Ultrasound Imaging

Carotid ultrasound is a reliable method to measure carotid intima-media thickness (cIMT; in mm), which has been shown to be increased in children with HoFH (Kusters, 2014). The technique has shown reliable results with an interobserver coefficient of variation of 7.3% (Doyon, 2013).

8.2.7. Pharmacodynamic Procedures

Total ANGPTL3 concentrations in serum will be measured using the PK samples collected at time points listed in [Table 3](#).

8.2.8. Future Biomedical Research

Research samples (serum/plasma) will be collected at time points listed in [Table 3](#). The unused biomarker samples for study-related research, as well as unused PK and ADA samples, will be stored for up to 15 years after the final date of the database lock. The unused samples may be utilized for future biomedical research of HoFH and other diseases. No additional samples will be collected for future biomedical research. After 15 years, any residual samples will be destroyed. The results of these future biomedical research analyses will not be presented in the Clinical Study Report.

8.2.9. Other Assessments

8.2.9.1. Review of Diet

Patients will be asked to follow a heart-healthy diet throughout the duration of the study, starting at the baseline visit and continuing through the end of the open-label treatment period (OLTP), until the last study visit. Patients will be queried on compliance with their diet at time points listed in [Table 1](#), [Table 2](#), and [Table 3](#).

Details are provided in [Appendix 1](#).

8.2.9.2. DNA Sample for HoFH Genotyping

A required blood sample for DNA isolation will be collected to identify or confirm a known mutation in PCSK9, LDLR, APOB, and/or LDLRAP1 gene. Genotyping will be done for patients who have not been enrolled previously in an evinacumab or alirocumab trial.

8.2.9.3. Genomics Sub-Study (Optional)

The genomic sample will be taken for patients who have not been enrolled previously in an evinacumab or alirocumab study. Patients who agree to participate in the genomics sub-study will be required to sign a separate genomics sub-study informed consent form (ICF) before collection of the samples. Patients are not required to participate in the genomics sub-study in order to enroll in the primary study. Samples for DNA extraction should be collected on day 1/baseline (predose), but may be collected at any study visit.

DNA samples for the genomics sub-study will be double-coded as defined by the International Council for Harmonisation (ICH) guideline E15. Sub-study samples will be stored for up to 15 years after the final date of the database lock and may be used for research purposes. The purpose of the genomic analyses is to identify genomic associations with clinical or biomarker response, other clinical outcome measures and possible AEs. In addition, associations between genomic variants and prognosis or progression of hypercholesterolemia as well as related diseases may also be studied. These data may be used or combined with data collected from other studies to identify and validate genomic markers related to the study drug and related diseases. Analyses may include sequence determination or single nucleotide polymorphism studies of candidate genes and surrounding genomic regions. Other methods, including whole-exome sequencing, whole genome sequencing, DNA copy number variation may also be performed. The list of methods may be expanded to include novel methodology that may be developed during the course of this study or sample storage period. Results from the genomic sub-study will not be reported in the CSR.

9. SAFETY DEFINITIONS, REPORTING, AND MONITORING

9.1. Obligations of Investigator

The investigator must promptly report to the IRB/EC all unanticipated problems involving risks to patients/subjects, according to local regulations. This may include death from any cause and all SAEs related to the use of the study drug. It is recommended that all SAEs be reported to the IRB/EC, according to local regulations.

9.2. Obligations of Sponsor

During the course of the study, the sponsor will report in an expedited manner all SAEs that are both unexpected and at least reasonably related to the study drug (suspected unexpected serious adverse reaction [SUSAR]), to the health authorities, IRBs/ECs as appropriate, and to the investigators.

Any AE not listed as an expected event in the Reference Safety Information section of the Investigator's Brochure will be considered as unexpected. Any worsening of or new onset of symptoms related to HoFH, which occur during the screening/washout period prior to study drug administration will be considered expected.

In addition, the sponsor will report all other SAEs to the health authorities, according to local regulations.

At the completion of the study, the sponsor will report all safety observations made during the conduct of the trial in the clinical study report to health authorities and IRBs/ECs as appropriate.

9.3. Definitions

9.3.1. Adverse Event

An AE is any untoward medical occurrence in a patient administered a study drug, which may or may not have a causal relationship with the study drug. Therefore, an AE is any unfavorable and unintended sign (including abnormal laboratory finding), symptom, or disease, which is temporally associated with the use of a study drug, whether or not considered related to the study drug.

An AE also includes any worsening (ie, any clinically significant change in frequency and/or intensity) of a pre-existing condition that is temporally associated with the use of the study drug.

9.3.2. Serious Adverse Event

An SAE is any untoward medical occurrence that at any dose:

- Results in **death** – includes all deaths, even those that appear to be completely unrelated to study drug (eg, a car accident in which a patient is a passenger).
- Is **life-threatening** – in the view of the investigator, the patient is at immediate risk of death at the time of the event. This does not include an AE that had it occurred in a more severe form, might have caused death.

- Requires in-patient **hospitalization** or **prolongation of existing hospitalization**. In-patient hospitalization is defined as admission to a hospital or an emergency room for longer than 24 hours. Prolongation of existing hospitalization is defined as a hospital stay that is longer than was originally anticipated for the event, or is prolonged due to the development of a new AE as determined by the investigator or treating physician.
- Results in persistent or significant **disability/incapacity** (substantial disruption of one's ability to conduct normal life functions).
- Is a **congenital anomaly/birth defect**.
- Is an **important medical event** - Important medical events may not be immediately life-threatening or result in death or hospitalization, but may jeopardize the patient or may require intervention to prevent one of the other serious outcomes listed above (eg, intensive treatment in an emergency room or at home for allergic bronchospasm; blood dyscrasias or convulsions that do not result in hospitalization; or development of drug dependency or drug abuse).

Criteria for reporting SAEs must be followed for these events. See Section 9.4 for more information on recording and reporting SAEs.

9.3.3. Adverse Events of Special Interest

An adverse event of special interest (AESI; serious or non-serious) is one of scientific and medical concern specific to the sponsor's product or program, for which ongoing monitoring and rapid communication by the investigator to the sponsor can be appropriate. Such an event might warrant further investigation in order to characterize and understand it. Depending on the nature of the event, rapid communication by the trial sponsor to other parties (eg, regulators) might also be warranted (Section 9.4.3).

9.3.4. Infusion Reactions

Infusion reactions are defined as any relevant AE that occurs during the infusion or within 2 hours after the infusion is completed. All infusion reactions must be reported as AEs (defined in Section 9.4.1) and graded using the grading scales as instructed in Section 9.5.1.

9.4. Recording and Reporting Adverse Events

9.4.1. Adverse Events

The investigator (or designee) will record all AEs that occur from the time the informed consent is signed until the end of study. Refer to the study reference manual for the procedures to be followed.

Information on follow-up for AEs is provided in Section 9.4.6. Laboratory, vital signs, or ECG abnormalities are to be recorded as AEs as outlined in Section 9.4.5.

9.4.2. Serious Adverse Events

All SAEs, regardless of assessment of causal relationship to study drug, must be reported to the sponsor (or designee) within 24 hours. Refer to the study reference manual for the procedure to be followed.

Information not available at the time of the initial report must be documented in a follow-up report. Substantiating data such as relevant hospital or medical records and diagnostic test reports may also be requested.

In the event the investigator is informed of an SAE after the patient completes the study, the following will apply:

- SAE with an onset within 30 days of the end of study or within 168 days (24 weeks) of last study drug administration if the patient early terminated from the study - the SAE will be reported to the sponsor. The investigator should make every effort to obtain follow-up information on the outcome until the event is considered chronic and/or stable.
- SAE with an onset day greater than 30 days from the end of study/early termination visit - only fatal SAEs and those deemed by the investigator to be drug-related SAEs will be reported to the sponsor. The investigator should make every effort to obtain follow-up information on the outcome of a drug-related SAE until the event is considered chronic and/or stable.

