6.3. Premature Withdrawal from the Study

A patient has the right to withdraw from the study at any time, for any reason, and without repercussion.

The investigator and/or sponsor have the right to withdraw a patient from the study if it is no longer in the interest of the patient to continue in the study, or if the patient's continuation in the study places the scientific outcome of the study at risk (eg, if a patient does not or cannot follow study procedures). An excessive rate of withdrawals would render the study uninterpretable; therefore, unnecessary withdrawal of patients should be avoided.

Patients who are withdrawn prematurely from the study will be asked to complete study assessments, as described in Section 8.1.4.

Rules for discontinuation of study treatment (permanent or temporary) are discussed in Section 7.3.2.

Early Termination from the Study

Patients who prematurely discontinue from study drug or the study should return to the clinic (within 5 days if possible), for end of treatment visit assessments. The assessments completed should include pregnancy testing for WOCBP. They should then return for all regularly scheduled study visits and complete all assessments except dosing of study drug.

If a patient is discontinuing the study and will not be able to return for all regularly scheduled study visits, at a minimum, they should return for end of study assessments at least 24 weeks after their last dose of study drug. All sexually active males and WOCBP should be reminded to continue to maintain highly effective contraceptive measures for 24 weeks after the last dose of study drug. At the end of treatment/early termination visit, all WOCBP will be provided with urine pregnancy tests with instructions to test for pregnancy 4 weeks after this visit and Q4W thereafter. Patients will also be notified of Q4W follow-up phone calls to confirm continued contraception use and pregnancy reporting and to obtain the results of the urine pregnancy test.

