Study Procedure	Q4-Week Visit Sequence ¹⁰				End of Treatment (4 weeks post last dose)/ Early Termination Visit ¹⁴	24-Week Follow-up Period				
	C	D	E	F		PV 8 weeks post last dose ¹⁵	12 weeks post last dose	PV 16 weeks post last dose ¹⁵	20 weeks post last dose	24 weeks post last dose/ End of Study Visit
Visit Window (Day)	±7	±7	±7	±7		F/U ±5	F/U ±5	F/U ±5	F/U ±5	F/U ±5
Treatment:										
Administer IV Open-Label Study Drug ³	X	X	X	X						
Concomitant Medications and Procedures including LMT and apheresis) ³	X	X	X	X	X	X	X	X	X	X
Efficacy:										
Lipid Panel ^{3,5}	X	X		X	X		X			X
Specialty Lipid Panel ^{3,5}		X		X	X		X			X
Safety:										
Adverse Events	X	X	X	X	X	X	X	X	X	X
Physical Examination										X
Measured Height ⁶				X	X					X
Body Weight	X	X	X	X	X					X
Vital Signs ⁴	X	X	X	X	X		X		X	X
Electrocardiogram ⁷				X	X					X
Tanner Stage ^{6,8}				X	X					X
Contraception Use Reminder	X	X	X	X	X	X	X	X	X	X

Study Procedure	Q4-Week Visit Sequence ¹⁰				End of Treatment (4 weeks post last dose)/ Early Termination Visit ¹⁴	24-Week Follow-up Period				
	C	D	E	F		PV 8 weeks post last dose ¹⁵	12 weeks post last dose	PV 16 weeks post last dose ¹⁵	20 weeks post last dose	24 weeks post last dose/ End of Study Visit
Visit Window (Day)	±7	±7	±7	±7		F/U ±5	F/U ±5	F/U ±5	F/U ±5	F/U ±5
Laboratory Testing²:										
Hematology		X		X	X		X		X	X
Blood Chemistry		X		X	X		X		X	X
Sex Hormones ^{6,8}				X	X					X
Serum Pregnancy Test ⁹					X					X
Urine Pregnancy Test ⁹	X	X	X	X		X	X	X	X	X
Urinalysis		X		X	X					X
hs-CRP		X		X	X					X
HbA1C	X			X	X		X			X
Research Samples				X	X					X
ADA Samples ¹⁰				X	X					X
Pharmacokinetics (PK) of Evinacumab ¹¹	X ¹²			X ¹²	X ¹²					X ¹²
Optional DNA Sample ¹⁶	X									
Other:										
Review of Diet	X	X	X	X	X	X	X	X	X	X
Reminder of LMT Compliance	X	X	X	X	X	X	X	X	X	X
Carotid ultrasound imaging ¹⁸				X						X

8.1.1. Footnotes for Schedule of Events Table 1

1. All evinacumab-naïve patients will enter the screening period. Patients who participated in a previous evinacumab study and who completed an end of study visit in the previous evinacumab study within 7 days prior to the baseline/day 1 visit for this open label study do not have to enter the screening period and may enroll directly in this study. Patients from previous evinacumab studies who do not enter this study within 7 days of completing the EOS visit of the previous study, must undergo screening.

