8.1.4. Early Termination Visit

Patients who are withdrawn from the study will be asked to return to the clinic for 2 visits: an end of treatment/early termination visit and an end of study visit. The end of treatment/early termination visit should take place within 5 days of treatment discontinuation, if possible. A final end of study (EOS) visit should take place with assessments as specified in the EOS visit at 24 weeks after the last dose of study drug described in [Table 3](#).

Sexually active patients who discontinue the study prematurely should be reminded to maintain highly effective contraceptive measures for 24 weeks after the last dose of study drug. At the end of treatment/early termination visit, WOCBP will be provided urine pregnancy tests with instructions to test for pregnancy Q4W until the EOS visit. All patients should also be notified of Q4W follow-up phone calls to confirm contraception use, remind them of pregnancy reporting, and to obtain the results of the urine pregnancy test. Patients who upon their study completion, may continue to receive treatment outside of the clinical trial (such as through a CUP, EAP, or ISS/IST) and thereby may forgo the 24-week follow-up period of the study. No off-drug follow-up period is required for these patients. In this situation, the patient's EOT will be their last study visit.

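### Protocol 9.4.2 gives two answers on reporting a late non-fatal, unrelated SAE in an early-terminated patient who has left the study (minor correction)

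*Protocol*

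**What the plan says.** Protocol 9.4.2 opens with a general duty: every SAE goes to the sponsor within 24 hours, whatever its causality. It then adds two bullets under one lead-in: "In the event the investigator is informed of an SAE after the patient completes the study, the following will apply".

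- First bullet: an SAE is reported if it starts no later than 30 days after the end of study, or if it starts "within 168 days (24 weeks) of last study drug administration if the patient early terminated from the study". There is no filter on causality or outcome.
- Second bullet: it covers an "SAE with an onset day greater than 30 days from the end of study/early termination visit". For these, "only fatal SAEs and those deemed by the investigator to be drug-related SAEs will be reported to the sponsor".

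The early termination visit is a separate visit from the EOS visit. Table 3 gives it its own column, "End of Treatment (4 weeks post last dose)/ Early Termination Visit", ahead of the follow-up columns. Section 8.1.4 says that withdrawn patients are "asked to return to the clinic for 2 visits: an end of treatment/early termination visit and an end of study visit", and on timing: "The end of treatment/early termination visit should take place within 5 days of treatment discontinuation, if possible". The EOS visit falls 24 weeks after the last dose. Of patients who leave the study and cannot attend all scheduled visits, section 6.3 says that "at a minimum, they should return for end of study assessments at least 24 weeks after their last dose of study drug".

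The TEAE period ends 168 days after the last open-label dose in both Protocol 10.4.4.1 and SAP 4.8.1.

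**The concern.** The second bullet names the early termination visit as a starting point for its 30-day clock. For an early-terminated patient that clock runs out long before day 168, where the first bullet's window ends. Between the two dates a non-fatal SAE judged unrelated is reportable under one bullet and not under the other. Neither document says which governs.

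The days in conflict belong to the TEAE period, and TEAEs are the primary endpoint. SAP 5.8.1 tabulates serious TEAEs and splits them into related and not related. A site that follows the second bullet would leave out events that a site following the first would send in, and the loss would fall only on the unrelated column. A single-arm study has no comparator that would show such a loss. Apart from the tables, a safety-reporting rule should not give sites two answers for the same event.

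**Working it through.** The plan states no figure on this point, so there is nothing to reproduce.

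**Step 1. Length of the overlap.** Let D be the day of the early termination visit, counted from the last dose. The second bullet starts on day D + 31 and the first bullet's window ends on day 168. The overlap is 168 − (D + 31) + 1 = 138 − D days.

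D is an assumption. Section 8.1.4 counts 5 days from treatment discontinuation, not from the last dose, and Table 3 footnote 14 puts the end of treatment visit 4 weeks after the last dose. I take D from 0 to 33 (33 = 28 + 5: the patient stops when the next dose is due and is seen 5 days later).

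| D | Days in conflict | Number of days |
|---|---|---|
| 0 | 31–168 | 138 |
| 5 | 36–168 | 133 |
| 28 | 59–168 | 110 |
| 33 | 64–168 | 105 |

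Every one of these days is on or before day 168, so all lie in the TEAE period. They are calendar days under conflicting rules for one affected patient, not days of lost data.

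**Step 2. Which events and patients are affected.**

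- Fatal SAEs and SAEs judged drug-related are reported under both bullets.
- Adverse events of special interest have their own 24-hour duty in 9.4.3.
- A patient still in follow-up is under the general rules of 9.4.1 and 9.4.2. One who attends the EOS visit is followed to about day 168.
- Table 3 footnote 15 has all patients phoned at weeks 8 and 16 after the last dose and asked about AEs.
- What remains is early terminators who miss the EOS visit and are no longer reached by those calls. For them AE collection ends at the last study visit (9.4.6), and 9.4.2 decides whether an SAE learned of later is reported.

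**Step 3. SAE rate.** Protocol section 1 reports 2 evinacumab patients (4.5%) with one SAE each in the 24-week double-blind period of R1500-CL-1629. Both events were judged unrelated and both resolved, so they are of the type at stake.

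- Patients: 2 / 0.045 ≈ 44.
- Patient-years: 44 × 168 / 365 = 20.25.
- Rate: 2 / 20.25 = 0.099 per patient-year.
- The exact 95% Poisson limits for 2 events are 0.242 and 7.225, which give 0.012 to 0.357 per patient-year.

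**Step 4. Expected events in the overlap.** The documents do not say how many patients will fall in the group left by step 2. I assume 1, 12 or 24 of about 120; 24 would mean that 20% terminate early and none is reached again. I also assume that every site follows the second bullet.

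Expected events = patients × (138 − D) / 365 × 0.099. The low end uses D = 33 and the high end D = 0.

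| Affected patients | Patient-years | Expected events | With the Poisson limits on the rate |
|---|---|---|---|
| 1 | 0.29–0.38 | 0.03–0.04 | 0.003–0.13 |
| 12 | 3.45–4.54 | 0.34–0.45 | 0.04–1.6 |
| 24 | 6.90–9.07 | 0.68–0.90 | 0.08–3.2 |

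**The case against.** The best defence is a harmonising reading. The section opens by requiring all SAEs, the first bullet gives a specific window for early terminators, and the second can be read as covering whatever the first leaves over. A sensible site might well read it so. But the text does not say it, and on that reading the second bullet's reference to the early termination visit has no effect for any such visit before day 138. If the second bullet governs instead, the 168-day limb shrinks to about 30 days after the visit. Either way, words in the protocol stop working. The objection softens the point without removing it.

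Three further objections stand:

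- Sections 9.4.1 and 9.4.2 send sites to the study reference manual, which was not supplied. It may state which bullet governs.
- Follow-up contact narrows the exposed group. Besides the phone visits that ask about AEs, sections 6.3 and 8.1.4 provide calls every 4 weeks (their stated purposes are contraception and pregnancy), and 6.3 asks for best efforts to establish the health status of patients who do not return. Missing the EOS visit does not by itself put a patient in the disputed group.
- The size leans high. It applies a rate from active trial follow-up to events that a site would learn of only after the patient had gone, and it assumes that all sites choose the narrower rule.

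A reader might infer that the trial loses some four months of SAE data for every early terminator, or that the primary safety tables are materially biased. The documents do not support either. Patients in follow-up remain under the general SAE rule, and the events that matter most for safety are reportable on both readings. Nor does the conflict reach completers. For them the first bullet runs to 30 days after the end of study and the second takes over from there. That includes patients moving to a compassionate use program, early access program or investigator-sponsored study, whose last visit is the end of treatment visit.

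**Conclusion.** The conflict is real and can be read directly from 9.4.2. For an early-terminated patient who has left the study, a non-fatal, unrelated SAE gets opposite answers if its onset is more than 30 days after the early termination visit and within 168 days of the last dose. The window is 138 − D days, or 105 to 138 days over the assumed range of D.

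The practical effect is small. The point estimate stays under one event in the trial even with 24 affected patients. Sampling error on a rate based on 2 events would allow about 1.6 events with 12 affected patients and 3.2 with 24. These figures rest on an assumed number of affected patients, the parent-study SAE rate, and every site following the second bullet. Confidence is medium, mainly because the study reference manual was not available. This is a minor correction to a reporting rule, not a threat to the interpretation of the study.

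**What to change.** Reconcile the two bullets for early-terminated patients only. For them, the second bullet's restricted reporting should start once the first bullet's window has ended: 168 days after the last dose, or 30 days after their last study visit if that is later.

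Leave the existing 30-days-after-end-of-study rule unchanged for completers. A general rule of 168 days for everyone would go too far. It would require all SAEs to be reported to day 168 for completers who move to a compassionate use program, early access program or investigator-sponsored study and may be receiving the drug outside the trial.

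The cost is about one sentence, with the same wording carried into the study reference manual. Protocol section 15 requires an IRB/EC-approved amendment, which is not worth raising for this alone in a multi-national study, so it should go into the next one. Sites may send in a few more SAE reports. The SAP needs no change, because its TEAE period already runs to 168 days after the last dose.
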